**Specific Aim 2. To compare the effects of antidepressant therapy HAPN activations following noxious visceral stimulation in IBS subjects based on the presence of somatization.**

Rationale: Case-control and randomized clinical trial data have established that somatization predicts symptom responses to IBS therapy with the tricyclic antidepressant desipramine. Specifically, IBS-S subjects are more refractory to antidepressant therapies, while IBS-No S subjects have better overall responses to the same treatment. A recent study has demonstrated improvements in HAPN visceral activations (anterior cingulate cortex) following desipramine therapy in an IBS cohort. Given these observations, the goal of this Aim is to assess whether differences in visceral HAPN activation patterns following desipramine treatment can be detected in IBS-S and IBS-No S subjects.

Design and Methods: The proposed study implements open-label desipramine therapy in 40 IBS (20 IBS-S and 20 age-matched IBS-No S) subjects. Participants from Aim 1 will be invited to continue on to open-label therapy in Aim 2. IBS-S and IBS-No S subjects will receive a 4-week treatment course with the tricyclic antidepressant desipramine (DES), as detailed in section 2.D., below. Subjects will undergo a fMRI protocol with noxious visceral and somatic stimuli as in Aim 1 at baseline, and then immediately following the 4-week desipramine therapy. Subjects will undergo baseline, and post-therapy assessment of psychiatric comorbidity (depression/anxiety) and IBS symptom severity (as described in 3.A. and 3.B., below). The primary endpoint is differences in visceral stimulation-induced brain activations of the HAPN on fMRI, ascertained between-groups following desipramine therapy. The proposed study design is outlined in Figure 9.

[figure not shown]
**Figure 9. Overview of study design for Specific Aim 2.** IBS patients with somatization (IBS-S) and without somatization (IBS-No S) will be identified. A baseline fMRI protocol (as in Aim 1) will be obtained at baseline, followed by a 4-week, open-label treatment with desipramine. A second fMRI protocol will be performed post-desipramine therapy at week 4. The primary endpoint of interest is post-treatment differences in visceral HAPN activations between IBS-S and IBS-No S subjects.

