**B. Sample size calculations.** The power calculations performed to assess the adequacy of the proposed sample size are based on the preliminary data, and are driven by the hypotheses proposed in Aim 2. These calculations assumed accrual of all subjects prior to the 10-week interval, a 10% attrition rate in each arm (2 subjects per group) over the course of the trial, observed group mean differences in blood flow within the anterior cingulate cortex from the IBS subjects studied in the Preliminary Studies section, and the previously reported post-desipramine reductions in ACC activations (effect size = 0.33). With the proposed sample size (n=20 per group), the anticipated 2-way ANOVA design examining the fMRI data with one between-subjects factor (Group) would be powered at 0.95 for detecting the anticipated difference using a conservative treatment effect size of 0.33, while assessment of Group x Treatment effect would be powered at 0.82 (figure 12). This sample size would allow the detection of a desipramine effect size of 0.25 at  $p<0.01$ , and also permit the interpretation of predicted non-significant interactions as consistent with the stated hypotheses. These power calculations were conducted using SamplePower v2.0 (SPSS, Inc).

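### The claim that the sample can detect a desipramine effect of 0.25 at p<0.01 is not supported by the 0.95 power at 0.33 stated beside it

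*Combined protocol and SAP*

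**What the plan says.** All the figures are in the combined protocol and SAP, Data Analysis and Sample Size Calculations, subsection B.

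- Sample size: "With the proposed sample size (n=20 per group), the anticipated 2-way ANOVA design". Aim 2 treats "40 IBS (20 IBS-S and 20 age-matched IBS-No S) subjects".
- Attrition: "a 10% attrition rate in each arm (2 subjects per group"). The paragraph does not say whether its powers use 20 or 18 per group.
- Effect inputs: "the previously reported post-desipramine reductions in ACC activations (effect size = 0.33"), together with "observed group mean differences in blood flow within the anterior cingulate cortex from the IBS subjects studied in the Preliminary Studies section", whose values are not given.
- First power: the design "would be powered at 0.95 for detecting the anticipated difference using a conservative treatment effect size of 0.33".
- Second power: "while assessment of Group x Treatment effect would be powered at 0.82".
- Sensitivity claim: "This sample size would allow the detection of a desipramine effect size of 0.25 at" p<0.01.

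No power is attached to the last sentence. The paragraph gives no alpha for the 0.95 or the 0.82. It also gives no sidedness, effect-size metric, standard deviation or pre/post correlation.

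**The concern.** The sentence offers a safety margin: an effect about a quarter smaller than the planning value (0.25 against 0.33) would be found, and at a stricter significance level. Both changes cost power, so a design with 0.95 at the planning effect has to give up a good deal to meet them.

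The margin is meant to be used. The same sentence goes on to rely on the sample size when reading non-significant interactions as agreeing with the hypotheses. The Aim 2 interpretation text also allows for differences smaller than expected, and for enrolling more subjects after power calculations. Overstated sensitivity would make a null result look more informative than it is.

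**Working it through.** **1. Can the plan's 0.95 be reproduced?** I used a noncentral F test with 1 numerator df, 20 per group and two-sided alpha 0.05 (assumed), at effect 0.33:

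- d: λ = (20/2) × 0.33² = 1.09, power 0.17.
- f, between subjects: λ = 40 × 0.33² = 4.36, power 0.53.
- f, two scans per subject, correlation 0: λ = 80 × 0.33² = 8.71, power 0.82 to 0.83. This matches the stated 0.82.
- f-squared: λ = 40 × 0.33 = 13.2, power 0.943.

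The 0.95 does not follow from the stated inputs alone. A within-subject f reaches it only with an added pre/post correlation of about 0.36 (20 per group) or 0.43 (18 per group). The rest of the check therefore takes 0.95 as given and asks what it implies for the sentence about 0.25.

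**2. Carry the 0.95 to 0.25.** On a d or f scale λ is proportional to the squared effect. Standard deviation and pre/post correlation cancel, provided both figures concern the same contrast.

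- λ giving 0.95 at alpha 0.05 on F(1,38): 13.69.
- At 0.25: 13.69 × (0.25/0.33)² = 13.69 × 0.574 = 7.86.
- Power at alpha 0.01: **0.542**. Power at alpha 0.05: 0.78.
- Other denominator df: 0.539 (34 df, 18 per group), 0.552 (76 df). Normal approximation: 0.562.

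**3. Effect with 80% power at p<0.01.** This needs λ = 12.78 on 38 df. The effect is 0.33 × √(12.78/13.69) = 0.32. For 80% power at 0.25 the sample would have to be 12.78/7.86 = 1.63 times as large.

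**4. Carry the 0.82 to 0.25.** λ = 8.71, and 8.71 × 0.574 = 5.00. Power at alpha 0.01 is 0.33. The effect with 80% power is 0.33 × √(12.78/8.71) = 0.40.

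**5. Vary what the plan leaves open, starting from 0.95 at 0.33.** At 0.25, λ is multiplied by 0.574 (d or f), by 0.25/0.33 = 0.758 (f-squared), or by (0.25/0.75)/(0.33/0.67) = 0.677 (eta-squared).

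| Scale | 0.95 at alpha 0.05 | 0.95 at alpha 0.01 |
|---|---|---|
| d or f | 0.54–0.55 | 0.73 |
| eta-squared | 0.63–0.64 | 0.82 |
| f-squared | 0.69–0.70 | 0.86 |

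Entries are two-sided power for 0.25 at p<0.01. If the 0.95 was at alpha 0.01, λ is 19.51, and on the d or f scale the effect with 80% power is 0.33 × √(12.78/19.51) = 0.27. Allowing one-sided tests as well, the d or f results run from 0.44 to 0.75.

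**The case against.** A reader might infer that the sentence contradicts the 0.95, or that no reading of the paragraph reaches 80%. The documents support neither.

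- **A consistent reading exists.** Take eta-squared, 40 subjects and alpha 0.01. Then λ = 40 × 0.33/0.67 = 19.7 gives 0.952, and λ = 40 × 0.25/0.75 = 13.3 gives 0.820. This reproduces the 0.95 and supports the claim. The only alpha printed in the paragraph is 0.01. However, the reading needs two unstated choices at once. It also makes a planning effect described as conservative equal to d = 2 × √(0.33/0.67) = 1.40, and with the planned 36 completers it falls to 0.92 and 0.76. The match between f = 0.33 at alpha 0.05 and the stated 0.82 points the other way, without proving it.
- **The contrasts may differ.** The 0.95 is attached to a design with a between-subjects factor, and preliminary group differences are a further input. The 0.25 is a desipramine effect. If the contrasts differ, λ cannot be carried across and 54% does not follow. This stands as a condition. Still, the paragraph itself calls the 0.33 a treatment effect and the reduction after desipramine, so a shared contrast is the natural reading. The 33% is weaker, because the 0.82 is explicitly for the interaction.
- **No power is claimed.** Read literally, an observed effect of 0.25 would reach p<0.01: the critical effect is 0.33 × √(7.35/13.69) = 0.24. That is true on these assumptions, but the sentence stands among power results. A true effect close to the critical value is found only about half the time, which is what the 54% says.
- **The power graph (Figure 13) is not visible in the text reviewed.** It may show the alpha or the scale, so its absence is not held against the plan.

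**Conclusion.** The sensitivity claim is unsupported. Its implied power is about 54%, given a d or f scale, the same treatment contrast for both figures, two-sided alpha 0.05 for the 0.95, and the 0.95 itself being correct. On a d or f scale no choice of alpha or sidedness examined brings power for 0.25 at p<0.01 up to 80%. Of the combinations examined, only eta-squared or f-squared with alpha 0.01 for the 0.95 does so, and the plan states neither element.

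A reader might also infer that the trial is too small for its main Aim 2 comparison. This check does not show that. It tests one secondary sentence against the figure beside it and takes that figure as given.

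**What to change.** Delete the sentence. Alternatively, replace it with the power for 0.25 recomputed from the original calculation for 18 completers per group, naming the alpha, sidedness, effect-size metric, pre/post correlation and contrast. Under the conventional assumptions above it should read about 54% at p<0.01 and 78% at p<0.05, conditional on the 0.95 being correct. These two figures should not be inserted without checking the original calculation, because the 0.95 cannot be rebuilt from what is printed. The same details should be given for the 0.95 and the 0.82.

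The cost is one or two sentences and one less favourable figure. The sample size does not change.

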**Figure 5. Proposed brain-gut interactions of IBS based on the presence of somatization.** It is hypothesized that IBS subjects with somatization, IBS-S (left panel) experience abnormal activations of the brain's homeostatic afferent processing network (HAPN) in response to visceral- and somatic afferent inputs. Thus, greater HAPN activations would be expected with both visceral and somatic stimuli in IBS-S. In contrast, IBS subjects without somatization, IBS-No S (right panel) likely have abnormal afferent signaling from the bowel as their primary neurosensory abnormality. IBS-No S subjects thus would be expected experience greater HAPN activations with visceral stimulation, but not with somatic stimulation. These hypotheses will be assessed in the Aims of this proposal.

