Analysis/interpretation: As a result of a more generalized abnormal pain response within the HAPN, it is hypothesized that IBS-S subjects will demonstrate greater activations of the HAPN with noxious somatic stimuli, compared to IBS no-S subjects and healthy controls. This hypothesis thus predicts a "IBS Group x Somatic stimulus" effect on two-way ANOVA analysis of activations within *a priori* HAPN regions. Specifically, it is hypothesized that the significantly increased HAPN activation pattern observed in IBS-S subjects compared to IBS-No S subjects that was observed following noxious visceral stimulation (preliminary data) will be present following noxious somatic stimulation in the IBS-S subjects, but not in the IBS-No S or healthy control groups (Figure 10, below). If this HAPN activation response to somatic stimuli is indeed observed in IBS-S subjects, it would support my hypothesis that in IBS-S patients, the presence of somatization reflects a less discriminate HAPN response to noxious stimuli, which includes not only visceral, but also somatic stimuli. This global overactivation of the HAPN in IBS-S subjects thus could have mechanistic relevance to the multiple pain experiences in affected individuals.

Alternately, if HAPN activation differences in IBS-S subjects are found only to be specific to visceral stimulation, the possibility that the HAPN is relevant to visceral, but not somatic, pain experiences in IBS-S subjects would be considered. This would imply that several distinct, system-specific sensory defects (i.e., gut, musculoskeletal, etc.) may be present in somatization, rather than the global pain processing abnormality within the HAPN as is hypothesized to be relevant to the multiple pain experiences of IBS-S subjects.

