(Delta S/S) will be the metric that is used. To statistically evaluate this, ROI analysis will be conducted in anatomically constrained areas along with voxel-by-voxel analysis. Both ROI-directed and voxel-by-voxel repeated measures ANOVAs (using parameters described below) are done across subjects using model estimates as inputs. Interaction effects and other activations resulting from specific comparisons of a subset of the events will be reported at an uncorrected threshold of  $p < 0.001$  for descriptive purposes. For the insular cortex, prefrontal cortex, orbitofrontal cortex, anterior cingulate cortex, and thalamic nuclei, predetermined ROIs will be used and will include any activations within these regions. A small volume correction will be applied, in keeping with the *a priori* hypotheses regarding these regions. Predetermined ROIs from the HAPN in Talairach space will be drawn using the Talairach atlas coordinate system^99 and the software ANALYZE™ will then be applied to all the participants. Regions which would not be expected to differ between the study populations will also be selected for analysis, and will provide internal activation standards to provide for the specificity of the findings (i.e., control regions). All selected ROIs will be used as a mask to constrain the regions in which test for differences are conducted. These regions will be used as a mask in an overlay on functional datasets to test the

hypotheses. Only areas with significant F-values on the ANOVA and falling within these regions will be used in statistical analyses. There will be 3 event types included in the model, resulting from the combination of all possible stimulus and response conditions: Visceral-Low distention (25-mm Hg), Visceral-High distention (50-mm Hg), and the Somatic stimulus. Voxel-by-voxel analyses will be conducted primarily to ensure that unpredicted differences a priori ROIs which are significant are not overlooked.

[figure not shown]

Figure 13: Study power as a function of sample size and effect.

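### The sample-size section lets predicted non-significant interactions be read as fitting the hypotheses, but no such interaction is named and the design cannot exclude moderate effects

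*Combined protocol and SAP*

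**What the plan says.** Section B, Sample size calculations (under Data Analysis and Sample Size Calculations), assumes 20 subjects per group, 10% attrition (2 per group) and an effect size of 0.33, to which it attaches power 0.95. It adds that "assessment of Group x Treatment effect would be powered at 0.82" and then: "This sample size would allow the detection of a desipramine effect size of 0.25", at p<0.01. The same sentence ends by saying that the sample size will "also permit the interpretation of predicted non-significant interactions as consistent with the stated hypotheses".

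The interactions and null expectations in the visible text are these:

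- **Aim 1, Analysis/interpretation:** an "IBS Group x Somatic stimulus" effect is predicted to be present. The raised somatic response is expected in IBS-S "but not in the IBS-No S or healthy control groups".
- **Figure 5 legend:** "IBS-No S subjects thus would be expected experience greater HAPN activations with visceral stimulation, but not with somatic stimulation".
- **Hypothesis 2 and Aim 2, Analysis/interpretation:** activation is expected to persist in IBS-S and to fall in IBS-No S, so Group x Treatment is predicted to be present.
- **Data Analysis:** "Regions which would not be expected to differ between the study populations will also be selected for analysis", as a check on specificity. These regions are not identified.

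**The concern.** A non-significant test is evidence of little or no effect only to the extent that the estimate is precise enough to exclude effects that matter. The clause goes from power at one assumed effect size to the interpretation of non-significant results, and it does not say which interactions it covers or how a null is to be judged. The visible text gives no smallest effect of interest, no margin and no rule based on an interval.

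The null expectations carry much of the interpretation. A generalised pain-processing abnormality specific to IBS-S needs the somatic response to be absent in IBS-No S and controls. Refractoriness to desipramine needs activation in IBS-S not to fall. Regional specificity needs the control regions not to differ. If imprecise results are accepted on these points because they are non-significant, the report could describe a pattern confined to IBS-S that the data do not establish.

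**Working it through.** **1. Is there a named interaction that is predicted to be null?** The visible text names two interactions, IBS Group x Somatic stimulus (Aim 1) and Group x Treatment (sample-size section). Both are predicted to be present. The predicted nulls are simple effects: no raised somatic response within two groups, no fall within IBS-S, and no group difference in control regions. The clause therefore has no stated referent. Figure 10 (anticipated findings) and the power figure are not shown and could not be checked.

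**2. Reproducing the 0.82.** Alpha, type of effect size and pre-post correlation (rho) are not stated. I assume Cohen's f, two-sided alpha 0.05 and two groups scanned twice. The noncentrality is f² x N x 2/(1 − rho), with 1 and 2n − 2 degrees of freedom.

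- n = 20 per group, f = 0.33, rho = 0: 0.1089 x 40 x 2 = 8.71, power 0.820.
- n = 18 per group, rho = 0: 0.1089 x 36 x 2 = 7.84, power 0.776. With rho = 0.1: 8.71, power 0.818.

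So 0.82 can be reproduced, but only on assumed inputs.

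**3. Precision, which needs no correlation.** In SD units the 95% half-width is t(0.975, df) x √(2/n) for two groups and t(0.975, df)/√n for one.

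| Contrast | n | Calculation | Half-width |
|---|---|---|---|
| Aim 1, two-group somatic comparison | 20 per group | 2.024 x √(2/20) | 0.64 SD |
| Aim 2, group difference in change | 18 per group | 2.032 x √(2/18) | 0.68 SD of change |
| Aim 2, change within IBS-S | 18 | 2.110/√18 | 0.50 SD of change |

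The 18 is 20 less the planned loss of 2 per group. Any correction across regions would widen these intervals.

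**4. How often a real moderate effect is non-significant.** From the noncentral t distribution, with an illustrative true effect of 0.5 SD:

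- Aim 1, 20 per group: noncentrality 0.5/√(2/20) = 1.58, non-significant 66% of the time.
- Within IBS-S, n = 18: noncentrality 0.5 x √18 = 2.12, non-significant 48% of the time.

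**5. What the 0.82 says about smaller interactions.** The section gives no separate effect size for the 0.82. Suppose it refers to an effect size e. The noncentrality that gives power 0.82 at n = 20 is 8.71, and at a true 0.25 it becomes 8.71 x (0.25/e)².

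| Assumed e behind the 0.82 | Noncentrality at 0.25 | Chance of missing a true 0.25 |
|---|---|---|
| 0.25 | 8.71 | 18% |
| 0.33 | 5.00 | 41% |
| 0.40 | 3.40 | 56% |
| 0.50 | 2.18 | 70% |

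To the precision shown, the miss rates are the same at 18 per group. The value 0.25 is the smaller effect size in the section, where it is given for the desipramine effect and not for the interaction.

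**The case against.** The best defence is that this is one subordinate clause in a sample-size paragraph and not a decision rule, and that a predicted non-significant result is literally consistent with the prediction. Both parts are fair. Nowhere does the plan say that absence will be claimed as proven, and its discussion of unexpected patterns is cautious. That limits the severity, but it does not supply the property that the clause attributes to the sample size.

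A reader might infer three stronger things, and the documents do not support them.

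- *That a null Group x Treatment result would count in favour of Hypothesis 2.* The clause covers predicted nulls, and this interaction is predicted to be present. If both groups improve and the group difference is not significant, Aim 2 treats this as a possible lack of power and considers further enrolment.
- *That the nulls are free to be chosen after the data are seen.* The main ones are written in advance, in Hypothesis 2, the Figure 5 legend and the analysis paragraphs of both aims. Only the control regions are left open.
- *That the planned test is known to miss a true 0.25 about 41% of the time.* That holds only if 0.82 refers to an interaction effect size of 0.33, which the section does not say. It also concerns Group x Treatment, which the clause does not cover. The half-widths are the more relevant figures.

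It can also be objected that formal equivalence testing asks too much of a small mechanistic study. I agree, and the fix does not require it.

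**Conclusion.** The concern holds as a point about interpretation. The clause claims something that the design does not provide: no interaction predicted to be null is named in the visible text, no rule for judging one is given, and power at an assumed effect is not evidence against smaller effects. A non-significant result would typically leave differences of about 0.5 to 0.7 SD within the 95% interval. The half-widths rest only on the planned numbers and the stated attrition. The 66% and 48% rest also on two-sided alpha 0.05 and an illustrative 0.5 SD. The 41% (18% to 70% over the range tried) rests on an assumed effect size behind the 0.82.

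The planned detection tests are not affected. The change should be made, because otherwise the conclusions about specificity and refractoriness may rest on imprecise nulls.

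**What to change.** 1. Delete the clause from section B.
2. State that non-significance will not be read as evidence of no difference or no change.
3. For each null expectation (somatic response in IBS-No S and controls, persistent activation in IBS-S, control regions), report the estimate in the plan's signal-change metric with a 95% confidence interval. Call the result inconclusive when the interval includes differences that matter.
4. Name the control regions before the data are analysed.

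A formal equivalence margin is optional and would rarely be met. With 18 per group and a true difference of zero, a 90% interval for the group difference in change lies inside ±0.5 SD of change in about 2% of trials, ±0.8 SD in about 52% and ±1.0 SD in about 81% (400,000 simulations). The documents give no SD for the metric, so a margin would need its own justification. The preliminary scans are one source, but they had only 8 subjects per group.

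The cost is a few sentences and intervals from models already planned, with no new data. The downside is that more results will be labelled inconclusive.
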